12.4.3 Handling of remaining intercurrent events of primary estimand

The primary analysis has incorporated all potential intercurrent events related to treatment or concomitant therapy as part of the treatment of interest attribute of the estimand and no other intercurrent events are necessary.

12.4.4 Handling of missing values not related to intercurrent event

Given that the participants in this clinical trial will be hospitalized for their participation, it is not expected that there will be any additional missing data in the primary analysis.

12.4.5 Sensitivity analyses for primary endpoint/estimand

The following sensitivity analyses will be performed for the primary estimand, to assess the robustness of the estimation in the presence of deviations from the assumptions specified in the primary analysis.

- In order to determine the robustness of the logistic regression model used for the primary analysis of clinical response at Day 15, a non-parametric regression model ([Koch et al 1998](#)) will also be evaluated using the same explanatory variables as the logistic regression model.

12.4.6 Supplementary analysis

No supplementary analysis are planned at this time.

12.4.7 Supportive analyses

The primary efficacy endpoint will be evaluated with respect to the following subgroups

- Age (18-65, > 65 years)
- SpO₂ (≤94% > 94%)
- Requiring supplemental oxygen at the time of randomization (No/Yes)

The primary estimand will be applied here to each of these subgroups variables adding the subgroup variable and treatment group by subgroup interaction to the model to evaluate whether there is any association between the level of subgroup variable and treatment.

12.5 Analysis of secondary estimands

Viral clearance at Day 15

The secondary efficacy endpoint of the percentage of participants with negative or below LLOQ - SARS-COV-2 based on PCR by Day 15 will be determined based on the PCR test that is performed at Day 6, Day 10, and Day 15/Day of discharge. Data available in the literature would indicate that when viral clearance is achieved, that participants will not reverse their viral clearance during the 15-day period. The endpoint will be evaluated in the FAS using a logistic regression model with treatment group and whether or not supplemental oxygen is required at randomization as explanatory variables. Odds ratios will be computed for each of active treatment comparisons to placebo. Based on what data is available from the evolving COVID-19 literature, it is anticipated that hydroxychloroquine plus azithromycin will have a greater viral response than hydroxychloroquine and thus will be tested first for the secondary endpoints in the closed testing procedure to preserve familywise Type I error rate at 0.05 two-sided.

The hypotheses in the closed testing procedure will be evaluated in the following order:

H₁: hydroxychloroquine plus azithromycin is not different to placebo with respect to the percentage of participants achieving clinical response by Day 15

H₂: hydroxychloroquine is not different to placebo with respect to percentage of participants achieving clinical response by Day 15

H₃: hydroxychloroquine plus azithromycin is not different to placebo with respect to the percentage of participants achieving viral clearance by Day 15

H₄: hydroxychloroquine is not different to placebo with respect to the percentage of participants achieving viral clearance by Day 15

Time to SARS-CoV-2 negativity/ Time to return to pre-morbid oxygen requirement /Time to discharge (or ready for discharge)

The event rates for these different endpoints will be estimated with Kaplan-Meier product-limit formula. Greenwood's formula will be used to estimate the variance of failure rates and to derive 95% Z-test based confidence intervals for the difference in event rates between active treatment groups and placebo.

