5.1 Inclusion criteria

Participants eligible for inclusion in this study must meet **all** of the following criteria prior to randomization:

1. Informed consent must be obtained prior to participation in the study
2. Adult patient \geq 18 years old
3. Severe Acute Respiratory Syndrome Coronavirus (SARS-CoV)-2 infection confirmed by polymerase chain reaction (PCR) test or rapid test from respiratory tract specimen (e.g. nasopharyngeal swab) within 4 days prior to randomization
4. Currently hospitalized or requiring hospitalization due to COVID-19 disease

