12.2 Participant demographics and other baseline characteristics

Demographic and other baseline data including disease characteristics will be listed and summarized descriptively by treatment group for all study participants in the FAS and safety set. Participant demographic and baseline characteristics will include: age, sex, race, ethnicity, height, weight, BMI, oxygen saturation (SpO₂), duration of symptom onset to randomization, duration from hospital admission to randomization, SARS-COV-2-RNA/viral load PCR test result (negative/positive), COVID-19 abnormal chest x-ray at baseline consistent with COVID-19 (No/Yes), requiring oxygen at randomization (No/Yes), [REDACTED].

Categorical data will be presented as frequencies and percentages. For continuous data, mean, standard deviation, median, minimum, and maximum will be presented. For selected parameters, 25th and 75th percentiles will also be presented.

Protocol-solicited medical history will be summarized by treatment group.

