12.8.2 Secondary endpoint(s)

Data available from recent studies published by [Gautret \(2020\)](#) would indicate that viral clearance for hydroxychloroquine plus azithromycin is high. In one study all participants receiving this combination therapy achieved viral clearance by Day 6. Participants receiving standard of care generally do not achieve a response rate higher than 50%. However, many of these studies are small and often not randomized. If one were to assume that hydroxychloroquine plus azithromycin has an 80% response rate by Day 15 and standard of care has a 50% response rate by Day 15, under this scenario, using the sample size justified for the primary efficacy endpoint, the 30% treatment difference corresponds to an odds-ratio of 4.0 and given 148 participants per treatment group. There will be more than 99% power to detect such a treatment difference.

13 Ethical considerations and administrative procedures

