2.6.2 Statistical hypothesis, model, and method of analysis

The number (%) of participants who achieved viral clearance by Day 6 and by Day 10 will be summarized. Analysis will be performed on the FAS.

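### Participants PCR-negative on the Day 1 swab stay in the viral-clearance analysis with no adjustment for baseline PCR, which inflates clearance and pulls the treatment effect toward none

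*Protocol*

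**What the plan says.** **Entry and testing (protocol).** Section 5.1 accepts either assay for eligibility ("PCR) test or rapid test from respiratory tract specimen"), done within 4 days before randomization. Section 8.2.1 has that test read locally. A positive result on Day 1 is not required. Table 8-1 schedules a further SARS-CoV-2 test on Day 1, and Section 8.3.2 sends post-screening nasopharyngeal samples to a specialist virology laboratory. The baseline characteristics in Section 12.2 include a "PCR test result (negative/positive" classification.

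**Analysis (protocol).** Under Section 12.1 the FAS leaves out only mis-randomized participants. Section 12.5 states: "The endpoint will be evaluated in the FAS using a logistic regression model with treatment group", plus supplemental oxygen requirement at randomization. Clearance is read from the PCRs at Day 6, Day 10 and Day 15 or discharge, and is assumed not to reverse within 15 days. Section 2.2 counts death as failure. The two clearance hypotheses, H3 and H4, come third and fourth in a "closed testing procedure to preserve familywise Type I error rate at 0.05 two-sided".

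**Assumed effect (protocol).** Section 12.8.2 supposes that "hydroxychloroquine plus azithromycin has an 80% response rate by Day 15 and standard of care has a 50% response rate by Day 15".

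**SAP.** The trial was halted with 20 randomized, one of them mis-randomized (Section 1.1). Section 2.6.2 states: "The number (%) of participants who achieved viral clearance by Day 6 and by Day 10 will be summarized", again in the FAS. Section 2.6.3 uses the last available PCR up to Day 10 and counts a participant with no post-dose PCR as not cleared. Section 5.4 says that no statistical models will be fitted.

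**The concern.** The objective is to show that treatment helps participants achieve viral clearance. Someone with no detectable virus before treatment has nothing to clear. The two tests can be days apart and may differ in assay, specimen and laboratory, so a positive eligibility test followed by a negative Day 1 swab is foreseeable. The two-category baseline entry in Section 12.2 allows for it.

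Such participants stay in the denominator, and on the no-reversal assumption they will usually also be in the numerator, in every arm. Randomization balances them in expectation, but balance does not prevent dilution: they add successes that carry little or no information about treatment. The reported percentage then mixes clearance on treatment with negativity at entry.

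This matters most when the true effect is smaller than planned. Section 12.8.2 itself says that the studies behind its rates are small and often not randomized. Section 12.5 expects a weaker viral response for hydroxychloroquine alone (H4), and no power is stated for that comparison.

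**Working it through.** **Inputs.** 148 per arm, 80% versus 50%, odds ratio 4.0 (Section 12.8.2: "the 30% treatment difference corresponds to an odds-ratio of 4.0 and given 148 participants per treatment group"); two-sided 0.05 (Section 12.5). The share q of each arm that is negative on Day 1 is not in the documents, so a range is assumed.

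**The plan's own figure.** Power = Φ[(|p1 − p0| − 1.96·√(2·p̄(1 − p̄)/n)) / √((p1(1 − p1) + p0(1 − p0))/n)], where p̄ is the mean of p1 and p0. With 0.80, 0.50 and n = 148 this is Φ[(0.30 − 1.96 × 0.0554)/0.0526] = Φ(3.64) = 99.99%. A Wald test on the log odds ratio gives 99.95%. Either agrees with the protocol: "There will be more than 99% power to detect such a treatment difference".

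**Dilution.** Suppose 80% and 50% are the rates among Day 1 positives and every Day 1 negative ends as cleared. The FAS rate in an arm is q + (1 − q)p, and the difference is (1 − q)(p1 − p0). At q = 20% the rates are 0.20 + 0.80 × 0.80 = 84% and 0.20 + 0.80 × 0.50 = 60%. The odds ratio is (0.84 × 0.40)/(0.60 × 0.16) = 3.50.

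| q | FAS rates | Difference (points) | Odds ratio | Power, FAS (n = 148) | Power, positives only (n = 148(1 − q)) |
|---|---|---|---|---|---|
| 0 | 80% v 50% | 30 | 4.00 | 99.99% | 99.99% |
| 10% | 82% v 55% | 27 | 3.73 | 99.9% | 99.96% |
| 20% | 84% v 60% | 24 | 3.50 | 99.7% | 99.9% |
| 30% | 86% v 65% | 21 | 3.31 | 99.0% | 99.7% |

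**Smaller effects (assumed; not in Section 12.8.2).**

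| Rates among positives | q | Power, FAS | Power, positives only |
|---|---|---|---|
| 70% v 50% | 0 | 94.4% | 94.4% |
| 70% v 50% | 10% | 90.1% | 91.9% |
| 70% v 50% | 20% | 84.3% | 88.6% |
| 70% v 50% | 30% | 76.8% | 84.1% |
| 65% v 50% | 0 | 74% | 74% |
| 65% v 50% | 20% | 59% | 65% |
| 65% v 50% | 30% | 51% | 59% |

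**How far 100% success among negatives drives this.** It gives the largest inflation of the percentages. If negatives succeed at rates s1 and s0 in the two arms, the difference is (1 − q)(p1 − p0) + q(s1 − s0). The tabulated difference is therefore the most diluted case as long as active treatment does no worse than placebo among negatives. It is unchanged for any common success rate. The odds ratio is not bounded in this way: at q = 20% with 90% success in both arms, the rates are 82% and 58% and the odds ratio is (0.82 × 0.42)/(0.58 × 0.18) = 3.30.

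**Type I error.** If p1 = p0 and treatment has no effect among negatives either, the expected difference is zero for every q.

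**SAP.** The FAS has 20 − 1 = 19 participants, or 19/3 ≈ 6.3 per arm if evenly split (the split is not given). One Day 1 negative counted as cleared is then worth about 1/6.3 ≈ 16 percentage points in its arm.

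**The case against.** **Success is not automatic.** A reader might infer that every Day 1 negative is a guaranteed success. The documents do not say so. A later negative PCR is still needed, death is a failure, and under the SAP so is having no post-dose PCR. A single negative swab may also be followed by a positive one. This stands, and it is why 100% success is treated above as an assumption.

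**The 80% and 50% may already include Day 1 negatives.** Section 12.8.2 applies them to all 148 per arm and does not restrict them to positives. On that reading the stated power needs no correction. The reported effect would still differ from the effect in people with virus to clear: at q = 20% the rates among positives would be (0.80 − 0.20)/0.80 = 75% and (0.50 − 0.20)/0.80 = 37.5%, an odds ratio of 5.0.

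**The Day 1 swab is not clearly a baseline measurement.** Section 8.2 requires baseline assessments before first dose. However, Section 8.3.2 treats the Day 1 swab as a post-screening efficacy sample, and Table 8-1 attaches its pre-dose note only to the ECG. SAP Section 2.1.1.3 takes baseline from before Day 1, apart from ECGs and screening visits held on Day 1. This stands: the timing must be fixed in writing before the result is used for adjustment or subsetting.

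**Restriction changes the question.** Section 2.2 defines the population by a positive test within 4 days before randomization, and the FAS analysis targets that population. Making Day 1 positives the main population is a debatable change of estimand. This also stands, and it argues for adjustment with a supportive subset.

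**The tests will not be run.** The SAP fits no model, so H3 and H4 are not tested. That confines the practical effect in the SAP to descriptive percentages, but those percentages are still exposed.

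**Conclusion.** The gap is real. Neither document gives a rule for participants negative on the Day 1 swab. They stay in the FAS, and on the protocol's no-reversal assumption most of them would count as cleared whatever their arm. Clearance is inflated, and the difference and odds ratio move toward no effect. If 80% versus 50% holds among positives and all negatives succeed, each 10% of negatives removes 3 of the 30 points.

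Two stronger conclusions do not follow. The first is that the plan's power claim fails: at the planned effect, power stays about 99% up to 30% negative. The second is that the test is invalid: Type I error is unaffected. Material power loss needs a smaller effect, which is an assumption here. With 70% versus 50% and 20% negative, power is 84% in the FAS against 89% in positives only, compared with 94% if there were no negatives.

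The actual share of Day 1 negatives is unknown, so the size is a range and not an estimate. In the SAP the consequence is limited to percentages in about 19 participants.

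**What to change.** **Protocol Section 12.5.** Keep the FAS analysis. State that the Day 1 swab is taken before the first dose and is the baseline PCR. Add that result as a covariate in the logistic model. If nearly all negatives clear, the covariate will show separation. The treatment odds ratio can still be estimated from the positives, but the plan should name a Firth-type penalty or an exact method for that case. Prespecify a supportive analysis in participants PCR-positive on Day 1.

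**Abbreviated SAP.** Report baseline PCR by arm. It does not appear among the legible entries in Section 2.3.2, although one entry there is blacked out. Tabulate the number and percentage cleared by Day 6 and by Day 10 according to Day 1 PCR result. Section 2.1.1.3 should name the pre-dose Day 1 swab as the baseline for PCR, as it already does for ECG.

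**Cost.** One covariate, one extra table and a few lines of wording. The swab is already scheduled. The supportive analysis has fewer participants, 148(1 − q) per arm under the planned design.

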12.5.1 Safety endpoints

For all safety analyses, the safety set will be used. All listings and tables will be presented by treatment group.

Safety summaries (tables, figures) include only data from the on-treatment period with the exception of baseline data which will also be summarized where appropriate (e.g. change from baseline summaries). In addition, a separate summary for death including on treatment and post treatment deaths will be provided. In particular, summary tables for adverse events (AEs) will summarize only on-treatment events, with a start date during the on-treatment period (treatment-emergent AEs).

The on-treatment period lasts from the date of first administration of study treatment to 30 days after the date of the last actual administration of any study treatment.

Adverse events

A treatment-emergent AE is defined as any AE that develops after initiation of the study treatments or any event already present that worsens following exposure to the study treatment.

All information obtained on adverse events will be displayed by treatment group and participant.

The number (and percentage) of participants with treatment-emergent adverse events (events started after the first dose of study medication or events present prior to start of double-blind treatment but increased in severity based on preferred term) will be summarized in the following ways:

- by treatment, primary system organ class and preferred term.
- by treatment, primary system organ class, preferred term and maximum severity.
- by treatment, Standardized MedDRA Query (SMQ) and preferred term.

Separate summaries will be provided for study medication related adverse events, death, serious adverse events, other significant adverse events leading to discontinuation.

A participant with multiple adverse events within a primary system organ class is only counted once towards the total of the primary system organ class.

Vital signs

All vital signs data will be listed by treatment group, participant, and visit/time and if ranges are available, abnormalities will be flagged. Summary statistics will be provided by treatment group and visit/time.

ECG

The overall interpretation of the ECGs will be summarized by treatment group and visit/time.

Any clinically significant changes in ECG parameters will be summarized by treatment group.

Summary statistics will be presented by treatment and visit/time, as appropriate.

Clinical laboratory evaluations

All laboratory data will be listed by treatment group, participant, and visit/time and if normal ranges are available abnormalities will be flagged. Summary statistics will be provided by treatment and visit/time. Shift tables using the low/normal/high/ (low and high) classification will be used to compare baseline to the worst on-treatment value.

12.5.2 Biomarkers

All biomarker data will be listed by treatment group, participant and visit. Summary statistics and graphical summaries (including spaghetti plots, boxplots and mean plots with SD) will be provided by treatment and visit. The number of values outside of the limits of quantification will be reported in each table. Values above the ULOQ will be imputed as ULOQ in graphical

summaries (with a special symbol) and for the calculation of the summary statistics. Values below the LLOQ will be imputed as LLOQ/2 for these analyses.

[REDACTED]

12.7 Interim analyses

No formal interim analysis is planned for this trial. The primary endpoint analysis will be performed after all participants have completed Day 15 or discontinued prior to Day 15. A final analysis will be performed after all participants have completed their last follow-up visit at Day 40 (or discontinued prior to Day 40).

12.8 Sample size calculation

12.8.1 Primary endpoint(s)

Assuming a true treatment difference in clinical response of 20% for hydroxychloroquine plus azithromycin plus SoC vs. placebo plus SoC, and an odds-ratio of at least 2.25, a sample size of 148 participants per treatment group (444 overall) provides at least 93% power that the primary analysis will be statistically significant at the two-sided 5% significance level. This holds for a variety of different assumptions with respect to treatment and clinical response rates.

These sample size assumptions were evaluated using East Version 6.4.

The sensitivity of different assumptions for clinical response rate for treatment and control groups and effect size on power are summarized in [Table 12-1](#).

Table 12-1 Sensitivity of sample size to different response rates for 148 participants per group (N=444) and treatment differences for level of significance alpha = 0.05

HCQ/HCQ plus AZ Response Rate (%)	Standard of care response rate	Odds Ratio	Treatment difference (%)	Power (%)
50	35	1.86	15	74

HCQ/HCQ plus AZ Response Rate (%)	Standard of care response rate	Odds Ratio	Treatment difference (%)	Power (%)
50	30	2.33	20	94
50	25	3.00	25	99
60	45	1.83	15	73
60	40	2.25	20	93
60	35	2.79	25	99
70	55	1.91	15	76
70	50	2.33	20	94
70	45	2.85	25	99

12.8.2 Secondary endpoint(s)

Data available from recent studies published by [Gautret \(2020\)](#) would indicate that viral clearance for hydroxychloroquine plus azithromycin is high. In one study all participants receiving this combination therapy achieved viral clearance by Day 6. Participants receiving standard of care generally do not achieve a response rate higher than 50%. However, many of these studies are small and often not randomized. If one were to assume that hydroxychloroquine plus azithromycin has an 80% response rate by Day 15 and standard of care has a 50% response rate by Day 15, under this scenario, using the sample size justified for the primary efficacy endpoint, the 30% treatment difference corresponds to an odds-ratio of 4.0 and given 148 participants per treatment group. There will be more than 99% power to detect such a treatment difference.

13 Ethical considerations and administrative procedures

13.1 Regulatory and ethical compliance

This clinical study was designed and shall be implemented, executed and reported in accordance with the ICH Harmonized Tripartite Guidelines for Good Clinical Practice, with applicable local regulations (including European Directive 2001/20/EC, US CFR 21), and with the ethical principles laid down in the Declaration of Helsinki.

13.2 Responsibilities of the investigator and IRB/IEC

Before initiating a trial, the investigator/institution must obtain approval/favorable opinion from the Institutional Review Board/Independent Ethics Committee (IRB/IEC) for the trial protocol, informed consent form, consent form updates, participant recruitment procedures (e.g., advertisements) and any other written information to be provided to participants. Prior to study start, the investigator is required to sign a protocol signature page confirming his/her agreement to conduct the study in accordance with these documents and all of the instructions and procedures found in this protocol and to give access to all relevant data and records to Novartis/Sponsor monitors, auditors, Novartis/Sponsor Quality Assurance representatives, designated agents of Novartis/Sponsor, IRBs/IECs, and regulatory authorities as required. If an

inspection of the clinical site is requested by a regulatory authority, the investigator must inform Novartis/Sponsor immediately that this request has been made.

13.3 Publication of study protocol and results

The protocol will be registered in a publicly accessible database such as clinicaltrials.gov and as required in EudraCT. In addition, after study completion (defined as last participant last visit) and finalization of the study report the results of this trial will be submitted for publication and posted in a publicly accessible database of clinical trial results, such as the Novartis clinical trial results website and all required Health Authority websites (e.g. Clinicaltrials.gov, EudraCT etc.).

For details on the Novartis publication policy including authorship criteria, please refer to the Novartis publication policy training materials provided to you at the trial investigator meetings.

